The main objective of this study is to evaluate the performance of the Composite Interference Screw for ACL reconstruction with hamstring tendons in terms of objective (clinical evaluation) and subjective (functional evaluation) IKDC score. In the one hand, the hypothesis is at least 70% of the patients who will undergo ACL reconstruction with CIS will improve their objective IKDC from C or D to A or B (normal or almost normal) at 7 months (± 1 month) post-surgery visit. In the other hand, our hypothesis is that the patients who will undergo ACL reconstruction with CIS will improve their subjective IKDC at least of 11 points at 7 months (± 1 month) post-surgery visit.

I.4. JUSTIFICATION OF METHODOLOGICAL CHOICES

After patient information, objective and subjective IKDC scores will be collected before the operation and 7 months ± 1 month after the operation and a clinical examination is scheduled 2 months ± 2 weeks after the operation.

All the examinations carried out are standard examinations, already integrated in the follow-up of the patients with lesion of the ACL according to the recommendations of good clinical practice.

The co-primary endpoint includes two main evaluation criteria to conclude on the efficacy of ACL reconstruction with CIS. The co-primary endpoint will be evaluated by objective and subjective IKDC scores recorded before surgery and at 7 months (± 1 month) post-operative follow-up visit. The IKDC scores after surgery will be compared to the IKDC scores pre-surgery to determine the efficacy of the ligament/graft fixation by the screw.

I.5. EXPECTED IMPACTS

The study will confirm the performance and safety of the CIS in anterior cruciate ligament ruptures and its acceptable benefit/risk balance.

II. OBJECTIVES AND OUTCOMES

II.1. PRIMARY OBJECTIVE AND CO-PRIMARY ENDPOINT

The main objective of this study is to evaluate the performance of the Composite Interference Screw for ACL reconstruction at 7 months (± 1 month) based on a co-primary endpoint including two main evaluation criteria:

- The objective IKDC score (clinical evaluation)
- The subjective IKDC (functional evaluation)

The co-primary endpoint will be recorded at two times:

- Before the operation (up to 4 months before surgery) (V-1)
- 7 months after the operation (± 1 month) (V3)

The IKDC scores recorded at V3 will be compared to the scores recorded at V-1.

II.2. SECONDARY OBJECTIVES AND ENDPOINTS

The secondary objectives of this study are

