In the case of a new medical fact, the Sponsor, will be responsible for reporting new facts to the authorities in accordance with national regulations, as follows:

- Inform without delay the ANSM about the new medical fact, at the following email address: [contact] with the following subject: Fait nouveau / trial number/ international non-proprietary name (INN) or substance code and including:
 - ID-RCB N°,
 - Title of the study protocol,
 - Protocol code number,
 - Summary of the new fact and urgent safety measures implemented if necessary,
 - All relevant information for the evaluation of the new fact.
- Inform without delay the director of the Agence Régionale de Santé (ARS; regional health agency) and the Ethics Committee (CPP).

Any follow-up information with regards to the new safety medical fact will be reported to the regulatory authorities within 8 calendar days, and details regarding the urgent safety measures set up will be sent within 15 days to the regulatory authorities.

VII. STATISTICAL ASPECTS

VII.1. SAMPLE SIZE DETERMINATION

The sample size required for the study was determined in order to obtain sufficient final statistical power considering the 2 main criteria (co-primary endpoint). The statistical power used to determine the sample size required for each of the 2 main criteria is 90% to obtain a final statistical power of at least 80%.

Subjective IKDC:

The minimum relevant difference expected in the change at 7 months on the functional IKDC score is 11 points and the standard deviation expected in the IKDC score at pre-surgery and at 7 months is 13 points. A total of 32 evaluable patients will be necessary to ensure a 90% power to detect a significant difference in the change at 7 months for two-sided test at the 5% level using paired Student t test.

Objective IKDC:

It is expected that 96% of patient will have modalities C or D before surgery [5]. Based on the investigator's experience, the proportion of total expected to shift from an IKDC modalities C or D to modalities A or B is 70% and proportion of total expected to shift from an IKDC modalities A or B to modalities C or D is 1%. A total of 11 evaluable patients will be necessary to ensure a 90% power to detect a significant difference for two-sided test at the 5% level using McNemar test.

In order to ensure sufficient statistical power for both comparisons, the larger of the two required sample size is planned to be included, i.e. 32 patients.

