However, to increase the estimate precision of the co-primary endpoint, 50 completed patients will be targeted. With 50 patients, a precision around 13% can be achieved for the objective IKDC score and 3.6 points for the subjective IKDC score. This sample size will provide a final statistical power for primary objective of 97%.

Accounting for a maximum of 10% dropouts or missing data, 56 patients should be recruited in the study.

VII.2. ANALYSIS SETS

Four populations will be defined:

- Screened population will include all patients entering the study,
- Safety Set (SS) population will include all patients who received the surgical intervention,
- Full Analysis Set (FAS) population will be defined by all patient who received the CIS product and in whom at least one efficacy information has been collected after the application of the CIS,

- Per-Protocol (PP) efficacy population will include all patients in FAS population without any major protocol deviation.

Remark: according to the ICH E9 recommendations, this subset of patients corresponds to a subset of the full “intention-to-treat” analysis set, being the Full Analysis Set (FAS).

VII.3. MISSING VALUES AND DROP-OUT

For the primary analysis (FAS analysis), in the case of a patient with missing data, the corresponding data will not be replaced.

For sensitivity analyses, some of the missing data may be replaced. It will be performed according to the following scenarios:

- Best-worst scenario: the missing data on the pre-surgery objective IKDC score will be considered with an objective IKDC score to A and missing data on the 7-months objective IKDC score will be considered with an objective IKDC score to D.
- Worst-best scenario: the missing data on the pre-surgery objective IKDC score will be considered with an objective IKDC score to D and missing data on the 7-month objective IKDC score will be considered with an objective IKDC score to A.
- Last Observation Carry Forward (LOCF) method: the missing data on the 7-months subjective IKDC will be replaced using LOCF method.

No other missing data will be replaced.

VII.4. STATISTICAL ANALYSIS

VII.4.1. GENERAL CONSIDERATION

A Statistical Analysis Plan (SAP) will be written by the biostatistician detailing the statistical analysis. This document will be approved and signed by the Sponsor and the Coordinating Investigator before the first database lock.

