Number and frequency of patients with protocol deviations will be tabulated.

Patients presenting major deviation will be excluded from the PP efficacy population and therefore will not be taken into account on the primary efficacy analysis in the PP population.

VII.4.2. ANALYSIS OF THE CO-PRIMARY EFFICACY ENDPOINT

According to the Food and Drug Administration (FDA) guidance for industry – Multiple endpoints in clinical trials and European Medicines Agency (EMA) Guideline on multiplicity issues in clinical trials, for conclude that the CIS is effective, it will be necessary to demonstrate an effect on each of the primary endpoints. However, there is only one result that is considered a study success, namely, that all of the separate endpoints are statistically significant. Testing all of the individual endpoints at the 0.05 level does not cause inflation of the Type I error rate; rather, the impact of co-primary endpoint testing is to increase the type II error rate.

The co-primary endpoint analysis will be performed on FAS population.

The scores recorded at 7 months (± 1 month) after surgery will be compared to the scores recorded before surgery. The intra-subject comparison will be the main judgement criteria of success.

The objective IKDC score will be dichotomised by combining modalities A and B and modalities C and D.

The objective IKDC score at 7-months visit will be compared to the objective IKDC score before surgery using McNemar test or Q Cochrane test (if expected sample size for the contingency cell are less than 4).

The subjective IKDC score at 7-months visit will be compared to the subjective IKDC score before surgery using paired Student test or Wilcoxon test (depend of normality assumption).

Sensitivity analyses using different analyses sets and missing data handling as described above will be performed as described in section “Missing values / dropouts”. The PP analysis will be considered as confirmatory analysis.

VII.4.3. ANALYSIS OF THE SECONDARY EFFICACY ENDPOINT

The visual clinical examination and the record of specific IKDC items performed during the 2-months visit will be summarized using descriptive statistics on the FAS population.

VII.4.4. SAFETY ANALYSIS

The safety analysis will be performed on SS population.

Safety endpoints will be AEs and SAEs all through the study.

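### Section I.3 hypothesises at least 70% improvers and an 11-point gain, but the only success rule (VII.4.2) tests against no change, so study success does not answer I.3

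*Protocol*

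**What the plan says.** Section I.3 (Research hypotheses) gives two hypotheses, both with a floor. The first is that "at least 70% of the patients who will undergo ACL reconstruction with CIS will improve their objective IKDC from C or D", the target grades being A and B at the 7-month visit. The second is that patients "will improve their subjective IKDC at least of 11 points at 7 months".

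Section VII.4.2 gives the decision rule. It states that "for conclude that the CIS is effective, it will be necessary to demonstrate an effect on each of the primary endpoints", and that "there is only one result that is considered a study success, namely, that all of the separate endpoints are statistically significant". It adds: "The intra-subject comparison will be the main judgement criteria of success". The tests are McNemar or Cochran's Q for the dichotomised objective score, and paired t or Wilcoxon for the subjective score, each comparing 7 months with pre-surgery.

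The figures 70% and 11 return only in VII.1 (and its copy in the synopsis), as planning values: "The minimum relevant difference expected in the change at 7 months on the functional IKDC score is 11 points" and "the proportion of total expected to shift from an IKDC modalities C or D to modalities A or B is 70" per cent. The same section raises the target from 32 to 50 completers for precision: "With 50 patients, a precision around 13% can be achieved for the objective IKDC score and 3.6 points for the subjective IKDC score". It gives 97% as the final power for the primary objective. Section VII.4.1 provides for 95% CIs of means and exact 95% CIs of percentages as descriptive statistics.

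**The concern.** A paired test of 7 months against pre-surgery has no change as its null hypothesis. Rejecting it shows that scores moved. It does not show that 70% of patients moved from C/D to A/B, or that the gain reached 11 points. Yet significance is the whole of the success rule, and VII.4.2 makes it the basis for concluding that the device is effective.

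The thresholds are not incidental. Section I.2 presents 11 points as the literature threshold for a clinically significant pre/post change, and XII.1 says the sponsor's main purpose for the data is regulatory. A report could state that the study succeeded, next to hypotheses of 70% and 11 points, when the trial's own interval rules one of them out. The 97% power is likewise power to reject no change, not power to support I.3.

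**Working it through.** **Inputs.** Two-sided 5% tests (VII.4.1); 90% power per criterion, 11 points, SD 13 at each visit, 70% improving, 1% worsening, 50 completers (VII.1). The protocol gives no within-patient correlation. I use two values for the SD of change: 13·√2 = 18.4 (correlation 0), which reproduces the stated n, and 13, which reproduces the stated precision.

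**The plan's own figures, as tests against no change**
- Paired t, gain 11, SD of change 18.4: power 0.897 at n = 31 and 0.906 at n = 32. The stated 32 reproduces.
- McNemar: n = [1.96·√0.71 + 1.2816·√(0.71 − 0.69²)]² / 0.69² = 10.8, so 11. The stated 11 reproduces.
- Power at n = 50: t test 0.986, McNemar above 0.999, jointly about 0.986, against the stated 97%.
- Precision at n = 50: 1.96·√(0.7·0.3/50) = 12.7%, and 1.96·13/√50 = 3.6 points. Both reproduce.

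So VII.1 is coherent, but only with no change as the null.

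**The least that counts as success at n = 50**
- Objective, nobody worsening, exact McNemar: p = 2·0.5^b. Five improvers give 0.0625; six give 0.031. For 6/50 = 12% the exact 95% CI is 4.5% to 24.3%. With one worsener, 8 improvers are needed. The uncorrected McNemar statistic, which equals Cochran's Q for two visits, is already significant at 4 improvers (p = 0.046).
- Subjective: the smallest significant mean gain is t(0.975, 49)·SD/√50 = 2.01·18.4/7.07 = 5.2 points, or 3.7 points with SD 13.

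**When the results contradict I.3**

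| Improvers out of 50 | Exact 95% CI | Against 70% |
|---|---|---|
| 27 | 39.3% to 68.2% | wholly below |
| 28 | 41.3% to 70.01% | compatible |
| 41 | 68.6% to 91.4% | compatible |
| 42 | 70.9% to 92.8% | wholly above |

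The subjective interval is significant yet wholly below 11 for mean gains of 5.2 to 5.8 points (SD 18.4) or 3.7 to 7.3 points (SD 13).

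**How often this would happen.** Assume 50% improve, 1% worsen and the true mean gain is 10, so both I.3 statements are false. Treat the endpoints as independent. McNemar is then significant almost surely. Binomial with n = 50: P(27 or fewer) = 0.760 and P(34 or fewer) = 0.997. The t-test parts are by simulation.

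| Event | SD 18.4 | SD 13 |
|---|---|---|
| Success declared | 0.96 | > 0.99 |
| Success, objective CI wholly below 70% | 0.760·0.964 = 0.73 | 0.760·1.00 = 0.76 |
| Success, both point estimates below 70% and 11 | 0.997·0.612 = 0.61 | 0.997·0.705 = 0.70 |
| Success, both CIs wholly below | 0.760·0.028 = 0.02 | 0.760·0.076 = 0.06 |

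With 60% improving and a gain of 11 (SD 18.4), success with the objective CI excluding 70% has probability 0.234·0.986 = 0.23. At the planned 70% it is about 0.01.

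**If I.3 were made the tested claim.** A lower limit above 70% needs 42/50, which has probability 0.018 when the true rate is 70%. A lower limit above 11 has probability 0.025 when the true mean gain is 11. The trial is not sized for that claim.

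**The case against.** The best defence is that 70% and 11 are simply the expected effects. I.3 belongs to the justification chapter, VII.1 uses both figures as planning values, and stating an expected effect while testing against no change is ordinary practice. VII.4.2 claims only an effect on each endpoint and never says that success confirms 70% or 11. The 95% CIs are planned and n was raised for precision, so a reader could make the comparison unaided. Detailed output belongs in the SAP, which is not at hand. The case of 6 improvers is a boundary far from likely data, and the larger probabilities rest on a chosen truth: the objective part falls from 0.76 at 50% improving to 0.23 at 60% and 0.01 at 70%.

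Much of this stands. The planning reading is plausible, the sample sizes are right, and contradiction by both intervals together is rare. But I.3 does not adopt that reading: it says hypothesis and sets a floor. The descriptive intervals play no part in the success rule and are not read against either figure. The hypotheses and the rule both stand in the protocol, so a SAP cannot properly reconcile them alone. The count of 6 does depend on the version of the test; the other version lowers it to 4, which strengthens the point.

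**Conclusion.** The concern holds and should be fixed. The tests, their nulls and the sample size are sound for showing improvement from pre-surgery, but they do not address the hypotheses as I.3 states them. At n = 50 with nobody worsening, success needs only 6 improvers (exact test) and a mean gain of 5.2 points (3.7 if the SD of change is 13). Under the assumed truth of 50% improving and a 10-point gain, success with an objective interval that excludes 70% has probability 0.73 to 0.76; at the planned values the figure is about 0.01. These probabilities assume independent endpoints and an SD of change between 13 and 18.4. The mismatch itself depends on none of these assumptions. I.3 also leaves open whether 11 points is a mean gain or each patient's gain.

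**What to change.** 1. In I.3, state that 70% and 11 points are planning expectations, as in VII.1, and that 11 refers to the mean change.
2. In VII.4.2 and the matching synopsis text, limit the conclusion from two significant tests to improvement from pre-surgery.
3. Report with the primary result the C/D-to-A/B proportion with its exact 95% CI and the mean change with its 95% CI, each read against 70% and 11. With 50 evaluable patients, 27 or fewer improvers excludes 70%, 28 to 41 is compatible with it, and 42 or more lies above it. Do not describe the I.3 hypotheses as confirmed on p-values alone.

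A formal rule that a lower confidence limit must exceed 70% or 11 is not proposed. It would be for the sponsor to justify, and it would need new assumptions and a new sample size.

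The cost is a few sentences and two intervals of a kind already planned. Tests, sample size and data collection do not change. The price is a more modest permitted conclusion.

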During pre-inclusion visit, the Investigator (a qualified individual) will ask the participant and/or the legal guardians/legal representative to participate in the research project and provide him/her/them with information regarding:

- The objective of the study
- The automatic processing of participant-related data that will be collected during the research project, and shall also specify the participant's right to access, object to, or rectify the data.

The Investigator (a qualified individual) will also ensure that the eligibility criteria are met. If a person agrees to participate, he or she will give their consent orally. His or her non-opposition to data use will be recorded on a signed form and stored in his or her medical file. The participant may, at any moment, oppose the use of his or her data as part of the research.

III.5. FOLLOW-UP VISITS

- V -1, pre-inclusion visit: -4 months to Day 0 (before surgery)
 - Check of inclusion/exclusion criteria
 - Patient Information: weight, height, affected knee (right, left)
 - Demographic data: Age, sex
 - Life habits: smoker, sport activities
 - Relevant medical and surgical histories
 - IKDC questionnaires (objective and subjective dimension)
 - Signature of the written consent
- V 0, inclusion visit: surgery
 - Check of inclusion/exclusion criteria
 - Batch number of CIS medical device
 - Medical device used for femoral fixation
 - Clinical indication (Double-Louped SemiTendinosus and Gracilis tendon (DLSTG), SemiTendinosus tendon (ST4) or Bone-Patellar Tendon-Bone (BPTB also called Kenneth Jones method)
 - AEs report
- V 1, follow-up visit: at discharge
 - AEs report
- V 2, follow-up visit: at 2 months (± 2 weeks)
 - Visual clinical examination: healing, walking test, quadriceps lock and articular amplitude
 - Several items of the objective IKDC questionnaire (Lachmann test and joint effusion items)
 - AEs report

III.6. END OF RESEARCH VISIT

- V 3, follow-up visit: at 7 months (± 1 month)
 - IKDC questionnaires (objective and subjective dimension)
 - AEs report

IV. STUDY POPULATION

IV.1. INCLUSION CRITERIA

1. Acute or chronic ACL deficiency with complete or partial lesion of the anteromedial bundle requiring primary reconstruction of the ACL with hamstring tendons
2. Males or Females aged 18 to 60 years
3. No history of surgery on the affected knee
4. Patients not under guardianship or judicial protection
5. Signature of non opposition form (consent of the patient)

IV.2. EXCLUSION CRITERIA

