V.1. DESCRIPTION OF SURGICAL TREATMENT FOR ACL RECONSTRUCTION (HAS RECOMMENDATIONS)

Intra-articular ligamentoplasty technique:

Ligamentoplasty is preferentially performed by arthroscopy taking into account the complete assessment of the articulation that it allows in the same operating greater rapidity of operative follow-up, decrease in morbidity, speed of recovery.

Which transplant?

- No prospective comparative study concludes on the use of the quadriceps tendon or fascia lata.
- Overall subjective and objective results are identical with transplant Bone-Patellar Tendon-Bone (BPTB technique also called Kenneth Jones technique) or the transplant using the Double-Louped Semitendinosus and Gracilis tendon (DLSTG technique).
- The anterior pains (of tendinous or neuropathic origin) and the flessum are more frequent with the BPTB than with the DLSTG but the impact on the level of sports recovery is equivalent between the two techniques. Previous pain can, however, have a professional impact (an activity requiring kneeling).

What fixation?

Patellar Bone-Tendon Bone (BPTB technique also called Kenneth Jones technique):

- The fixation with a femoral interference screw and a tibial interference screw is the reference technique.
- Double fixation to the femur or tibia is useless unless the screw is held poorly interference (especially in the tibia).
- The screw can be metallic or bioresorbable.
- The bioresorbable screw has the advantage of facilitating the reading of a possible postoperative MRI and possible surgical revision.

Double-Louped SemiTendinous and Gracilis tendon (DLSTG technique):

- In the femur, it can use an extra-anatomic system, an interference screw or any other intraductal system. To date, no study recommends a double femoral fixation.
- In the tibia, the traction is in the axis of the transplant. This can lead to propose, especially when the bone behaviour is poor, a double fixation or strengthened.

Lateral tenodesis:

- Regardless of age, isolated lateral tenodesis is not recommended.
- There is no indication to perform systematic associated lateral tenodesis, in front of chronic anterior laxity.
- Lateral tenodesis associated with intra-articular reconstruction cannot be considered only in the context of an overall previous laxity.

V.2. DESCRIPTION OF THE PRODUCT

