The Composite Interference Screw (CIS) manufactured by Biomatlante is sterile, resorbable and osteoconductive of synthetic origin. The Composite Interference Screw is in the form of a cannulated screw:

Figure 1: Composite Interference Screw

The Composite Interference Screws are available in different diameters (from 7 to 12 mm), and several different lengths depending on the diameters (from 20 to 35 mm). Different diameters and lengths of implants are available to allow adaptation to the bone site but also to the patient's anatomy.

The design is suitable for easy installation, without tissue damage (self-tapping thread and atraumatic head).

These resorbable fixation systems are intended to be fully absorbed by the body during the process of bone healing.

They consist of:

- a polymer: poly (L-lactic-co-D, L-lactic acid) (PLDLLA)
- calcium phosphate granules (Hydroxyapatite and Béta Tricalcium Phosphate)

The polymer / granule ratio of calcium phosphate used here is 75% / 25%.

V.3. INTENDED USE

The Composite Interference Screw is intended to be used for knee ligament reconstructions.

The claimed performance for the Composite Interference Screw is as follows: fixation of the ligament/graft within the bone tunnel until bone consolidation is complete.

V.4. SURGICAL INDICATION

The Composite Interference Screw is indicated for torn ligaments in the knee.

The Composite Interference Screw is reserved exclusively for adults. The material has not been tested on pregnant or breastfeeding women.

V.5. CHOICE OF TREATMENT IN THE STUDY

Recruited patients will have an indication of ACL reconstruction with a tendon graft from hamstring muscles:

- DLSTG (Double-Louped SemiTendinosus and Gracilis) technique: use of tendon grafts from the Double-Louped SemiTendinosus and Gracilis muscles
- ST4 (SemiTendinous) technique: use of a tendon graft only from the SemiTendinosus muscle.

In the femur, the fixation will be assured by an intraductal system (Endobutton) and the composite interference screw will be used for the tibial fixation only. The indication of treatment (surgical or otherwise) after ACL injury will not be influenced by the study and will be performed according to good clinical practice.

Patients for whom a patellar tendon (BPTB technique also called Kenneth Jones technique) is advised by the surgeon according to good clinical practice will not be included.

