For medical information, the latest version at the time of study start of the Medical Dictionary for Regulatory Activities (MedDRA) for medical history and adverse events will be used.

IX.4.5. DATA VALIDATION

Validation checks programmed within the EDC system, as well as supplemental validation performed via review of the downloaded data, will be applied to the data in order to ensure accurate, consistent, and reliable data. Data identified as erroneous, or data that are missing, will be referred to the investigative site for resolution through data queries.

The eCRFs panel for each patient will be electronically signed by the Investigator.

IX.5. PROTOCOL DEVIATION

A protocol deviation is any noncompliance with the clinical trial protocol, International Conference on Harmonisation Good Clinical Practice (ICH GCP), or manufacturer recommendation requirements. As a result of deviations, corrective actions are to be developed by the site and implemented promptly. It is the responsibility of the site investigator to use continuous vigilance to identify deviations. All deviations must be reported in study source documents.

Examples of protocol deviations are presented below (non-exhaustive list):

- The screw has not been installed,
- Violation of inclusion/non-inclusion criteria,
- Post-inclusion protocol violation,
- Non compliance with visit scheduled

All protocol deviation will be listed before the data review meeting and reviewed during this meeting and classified as “minor” or “major”.

Number and frequency of patients with protocol deviations will be tabulated.

IX.6. AUDIT AND INSPECTION

Individuals appointed by the sponsor and independent of those conducting the study may carry out audits at any moment. The audit is designed to check the safety of the participants and the respect of their rights, compliance with applicable regulations and data reliability.

An inspection may also be undertaken by a competent authority (ANSM in France or EMA within the framework of a European study, for example).

The audit, as well as the inspection, may be applied to any stage of the research, from protocol development to the publication of results and the classification of data used or produced as part of the research project.

The investigators shall comply with the sponsor’s requirements regarding the audit and the competent authority’s inspection of the research.

X. ETHICAL AND REGULATORY CONSIDERATIONS

X.1. COMPLIANCE WITH REFERENCE TEXTS

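### The V0 visit lists BPTB although the study is limited to hamstring grafts, and the Safety Set counts operated patients who received no screw (minor)

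*Protocol*

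**What the plan says.** On the graft, the protocol speaks in two ways.

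- Inclusion criterion 1 (IV.1 and synopsis) admits patients "requiring primary reconstruction of the ACL with hamstring tendons". The synopsis entry on surgical technique and section V.5 name only DLSTG and ST4, and the main objective in I.3 is also worded for hamstring tendons.
- V.5 adds that a patient for whom a patellar tendon graft "is advised by the surgeon according to good clinical practice will not be included".
- III.5, under V0 (called the inclusion visit), has the site record the clinical indication. The options are DLSTG, "SemiTendinosus tendon (ST4) or Bone-Patellar Tendon-Bone (BPTB". Nothing there marks the third option as a failure of eligibility, although the same visit repeats the eligibility check.

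On the analysis sets, VII.2 of the protocol says:

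- FAS: this "population will be defined by all patient who received the CIS product" and who has at least one later efficacy value. It sets no graft condition.
- Safety Set: "Safety Set (SS) population will include all patients who received the surgical intervention". Receipt of the screw is not required.

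The secondary objective in II.2 is the safety of the screws. IX.5 gives as its first example of a deviation: "The screw has not been installed". VII.4.4 runs the safety analysis on the Safety Set, centres reporting on TEAEs, and defines a TEAE by its emergence or worsening after the product is introduced.

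**The concern.** There are two separate defects.

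**Status of BPTB.** An eCRF built from III.5 would offer BPTB as an ordinary choice. A site following III.5 and a site following V.5 would treat the same patient differently. At the data review meeting, where deviations are graded minor or major, the protocol does not settle whether a BPTB patient who received the screw violated it. That decides whether the patient can be removed from the PP set. It also decides whether the patient's presence in the FAS, on which the co-primary analysis runs, is reported as an exception or passes as normal.

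**Safety denominator.** The population is fixed by the operation, while the event is fixed by exposure to the device. An operated patient without a screw adds one to the denominator of every TEAE rate and cannot add to any numerator. The error runs in one direction only: it makes the device look safer. A post-operative event in such a patient also has no proper place in the summary tables, because it cannot be a TEAE.

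**Working it through.** **1. Graft: the passages side by side**

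| Place in protocol | Grafts covered |
|---|---|
| Synopsis, surgical technique | DLSTG, ST4 |
| I.3, main objective | hamstring tendons |
| IV.1, inclusion criterion 1 | hamstring tendons |
| V.5, choice of treatment | DLSTG, ST4; patients advised BPTB not included |
| III.5, V0 clinical indication | DLSTG, ST4, BPTB |

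Four places agree and III.5 departs from them. Take a patient with a BPTB graft who received the CIS and has a later efficacy value. The FAS wording in VII.2 admits this patient. The PP set removes the patient only if the graft counts as a major deviation. V.5 suggests that it is a deviation, whereas III.5 lists it as an indication. The text does not settle the matter.

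**2. Safety denominator**

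Inputs from the protocol: 50 completed patients targeted and up to 10% dropout (VII.1). The planned recruitment reproduces: 50 / 0.90 = 55.6, rounded up to 56.

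Assumptions, because the protocol gives no figures for them: all 56 are operated; k of them receive no screw; the true TEAE rate among patients with a screw is r.

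Patients with a screw: 56 − k. Patients with the event: r × (56 − k). The Safety Set divides by 56, so

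reported rate = r × (56 − k) / 56 = r × (1 − k/56).

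The relative loss is k/56, whatever the event:

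- k = 1: 1/56 = 1.8%
- k = 3: 3/56 = 5.4%
- k = 5: 5/56 = 8.9%

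| True rate r | k = 1 | k = 3 | k = 5 |
|---|---|---|---|
| 5% | 4.9% | 4.7% | 4.6% |
| 10% | 9.8% | 9.5% | 9.1% |
| 20% | 19.6% | 18.9% | 18.2% |

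Example: 10% × 53/56 = 9.46%, reported as 9.5%.

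The FAS requires receipt of the CIS, so a patient without a screw never reaches the co-primary analysis. This second defect touches safety only.

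**The case against.** The best defence is that neither case should occur often. V.5 keeps BPTB patients out, eligibility is checked at V-1 and again at V0, and IV.3 says that all recruited patients will receive the screw. Recording the graft at V0 is also how a wrong graft would be detected. IX.5 lists violation of the inclusion criteria and a screw not installed as deviations, and patients with major deviations leave the PP set. All of this stands, and it makes the point conditional and small. It does not remove the contradiction in III.5, and the PP set does nothing for the safety denominator.

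Three stronger readings are tempting, but the documents do not support them.

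- *A reader might infer that BPTB patients would bias the IKDC results.* V.1 does say that anterior pain and flessum "are more frequent with the BPTB than with the DLSTG". The bullet before it says that overall subjective and objective results are the same with the two grafts, and the sentence itself goes on to call the effect on sports recovery equivalent. On the protocol's own text, no net shift in either co-primary measure is to be expected.
- *A reader might infer that each BPTB patient moves the objective response by 2 points (1/50), so that five move it by 10.* That is not the shift from the planned 70%. With 70% in the other 45, five failures give 31.5/50 = 63% and five successes give 36.5/50 = 73%, so the extremes are −7 and +3 points. For one patient they are 34.3/50 = 68.6% and 35.3/50 = 70.6%, or −1.4 and +0.6.
- *A reader might infer that the FAS is wrongly defined.* Keeping treated patients despite an eligibility violation, with a PP analysis alongside, is ordinary practice. Excluding patients by the graft used at surgery would be a trade-off, not a correction.

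**Conclusion.** Both parts hold, and both are minor. First, III.5 conflicts with inclusion criterion 1, the synopsis, the I.3 objective and V.5. As a result, the status of a BPTB patient with a screw is undefined. No numerical effect on the co-primary endpoints is claimed. Second, the Safety Set is defined by surgery while TEAEs are defined by introduction of the product, and this mismatch can only lower device TEAE rates. Its size is k/56 in relative terms: about 1.8% for one patient without a screw and about 5.4% for three. The number of such patients is an assumption. If there are none, the rates are unaffected. The planned sample size and power do not depend on either part.

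**What to change.** 1. Reconcile the V0 entry in III.5 with inclusion criterion 1, the synopsis, the I.3 objective and V.5. If BPTB stays on the V0 form, mark it there as an eligibility failure or deviation, consistently with V.5.
2. In VII.2, define the Safety Set, or at least the denominator for TEAE rates, as all patients in whom placement of a CIS was done or attempted. State in VII.4.4 that an attempted placement counts as introduction of the product; otherwise attempted-only patients recreate the same mismatch.
3. List operated patients without a CIS, with all their adverse events, separately, so that nothing is lost from view.

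The FAS definition can stay as it is. The cost is a few words in III.5, VII.2 and VII.4.4 and one eCRF option. The downside is that a few patients may leave the safety denominator; the separate listing keeps them visible.
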